4 STUDY DESIGN

4.1 OVERALL DESIGN

Study Design:

This study is an unblinded, controlled randomized, 2-arm clinical trial.

Hypotheses:

Primary Hypothesis: We hypothesize that acupuncture will improve the quality of life in MG patients.

Secondary Hypothesis: We hypothesize that acupuncture will improve activities of daily living in MG patients.

Randomization:

Prior to the first acupuncture treatment visit, participants will be randomized into two treatment groups. Randomization is explained in **Section 6.3**.

Acupuncture Treatment Groups:

Group 1: 10 participants will receive acupuncture treatment immediately 2x per week for 12 weeks = 24 total.

Group 2: After a 12-week delay, 10 participants will receive acupuncture treatment 2x per week for 12 weeks = 24 total.

Study Intervention:

Acupuncture treatment will consist of a standardized treatment protocol designed for this study. Approximately 23-32 needles will be inserted into specific areas of the body for a duration of 30 minutes. Additional details of the treatment are discussed in **Section 6.1**.

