6.1.2 ADMINISTRATION AND/OR DOSING

Acupuncture Treatment Methods:

Group 1 will receive twice-weekly acupuncture immediately over 12-weeks. After a 12-week delay, Group 2 will also receive twice-weekly acupuncture over 12-weeks. Acupuncture treatments will be separated by a minimum of 2 days and a maximum of 14 days, unless a participant has an illness, such as COVID-19. In this case, additional time may be allowed, as determined by the investigator. Treatment methods will be identical for both groups and are described below.

Standard, sterile stainless-steel, disposable needles (DongBang™ Corporation, Spring Ten 0.22 x 30mm; Boryeoung, Republic of Korea) will be inserted in the acupuncture point locations (described below), with approximately 23-32 needles used for each treatment session. The number of needles used will be based

on the patient-reported symptoms. The depth of the needle insertion will be approximately 10-20mm, depending on the region of the body undergoing treatment. Needle reaction (soreness, numbness or distended feeling around the point, also known as a Deqi sensation) will occur during the initial insertion. Following 10 minutes of retention, some of the needles will be rotated in order to maintain Deqi sensation. Maintaining Deqi sensation has been shown to increase the effectiveness of acupuncture.^{10,11} All needles will be left in place for a total of 30 minutes, which is a typical duration in acupuncture practice.

Acupuncture points were selected for their classical Traditional Chinese Medicine indications relevant to MG symptom pathology, as well as their modern biomedical muscular, immunological, and neurological actions. The anatomical location for each point will be based on the World Health Organization's acupuncture point guideline.¹² Traditional Chinese manual acupuncture will be used at up to 32 acupuncture points. During treatment, acupuncture needles can be removed due to extreme pain or discomfort, so as not to exceed the removal of more than 4 needles.

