7.2 PARTICIPANT DISCONTINUATION/WITHDRAWAL FROM THE STUDY

Participants are free to withdraw from participation in the study at any time upon request. An investigator may discontinue a participant from the study for the following reasons:

1. Participant has not completed an acupuncture treatment for > 14 days, unless a participant has an illness, such as COVID-19. In this case, additional time may be allowed, as determined by the investigator.
2. Significant study intervention non-compliance
3. Lost-to-follow up; unable to contact subject (see **Section 7.3, Lost to Follow-Up**)
4. Any event or medical condition or situation occurs such that continued collection of follow-up study data would not be in the best interest of the participant or might require an additional treatment that would confound the interpretation of the study
5. The participant meets an exclusion criterion (either newly developed or not previously recognized) that precludes further study participation

The reason for participant discontinuation or withdrawal from the study will be recorded on the relevant eCRF. Subjects who sign the informed consent form and are randomized but do not receive the study intervention may be replaced. Subjects who sign the informed consent form, and are randomized and receive the study intervention, and subsequently withdraw, or are discontinued from the study, will not be replaced.

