9.2 SAMPLE SIZE DETERMINATION

We anticipate enrolling 10 subjects in each study group. The primary analysis is a two-sided two sample t-test comparing the mean change in MG-QOL15 over 12-weeks weeks from a delayed start 2-group design. We hypothesize that Group 1 who received acupuncture treatment will experience a change in QOL over the 12-weeks while Group 2, the untreated control, will not. We will analyze the data such that the opposite could be shown. The null hypothesis is that there will be no difference between treatment

groups. Our sample size of 10 subjects in each group achieves 80% power at a 5% significance level to detect a 1.32 SD difference in mean change in MG-QOL15 between groups (PASS software version 11). No interim analyses are planned. The potential effect on our power if for a range of true effect sizes are displayed in the table below. If our final analysis shows a smaller effect size than 1.32 SD difference, we will include and post-hoc power analysis with the results.

N	δ/σ	Power	Alpha
20	0.9	0.44	0.05
20	1.0	0.56	0.05
20	1.3	0.78	0.05
20	1.6	0.91	0.05

N = total sample size, 1:1 Randomization to 2 groups;

δ = treatment effect (change);

σ = standard deviation.

Based on preliminary estimates, we do not anticipate difficulty recruiting 20 subjects. HealthPartners clinicians see approximately 4 individuals with MG per month at the Neuroscience Center and Park Nicollet Clinics, approximately 50 annually. Therefore, we will need a 40% enrollment rate to reach our recruitment goal in the allotted time frame. In addition, we also plan to recruit and enroll from other HealthPartners clinics and within the community. If we see a 20% reduction in sample size due to dropout, withdrawal, or missing data, our power will be 71% to detect a similar effect size. This, and other possible changes in power due to attrition, are listed in the table below. *Note: The original sample size estimation was for 20 individuals; however, we wrote the protocol so that we could replace anyone who did not start the intervention. Thus, we are increasing the enrollment target to 25, which is not reflected in the original power analysis.

N	δ	σ	Power	Alpha
16	9.5	7	0.71	0.05
18	9.5	7	0.77	0.05
20	9.5	7	0.82	0.05

N = total sample size; δ = treatment effect (change); σ = standard deviation.

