9.3 POPULATIONS FOR ANALYSES

All analyses will be performed on an intention-to-treat basis. If poor attendance at acupuncture treatments is observed, we will perform a per-protocol analysis as a sensitivity analysis.

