9.4.2 ANALYSIS OF THE PRIMARY ENDPOINT(S)

The MG-QOL15 scores will be collected for each participant at several time points. The primary outcome, change in MG-QOL15 scores over the first 12-weeks, will be calculated using the first and second collected scores for both groups. Group 1 will have received the full acupuncture intervention between the two measurements while Group 2 will act as the untreated control. We will present the mean change by group with corresponding standard deviations. Analysis of covariances (ANCOVA) with adjustment for baseline MG-QOL15 and covariates identified above will be used to determine if a significant ($p<0.05$) intervention effect is present. If the model identifies a significant difference in change of MG-QOL15 associated with acupuncture treatment, next steps will assess if this change is still present 12-weeks after completing the full acupuncture treatment. Using data from Group 1, a paired t-test will be used to compare the MG-QOL15 scores directly after treatment (Post-treatment Assessment 1) and scores 12-weeks post-treatment (Post-treatment Assessment 2). (Refer to Schema on page 4 for data collection points.)

Prior to analysis, we will plot our outcomes to examine their distribution and decide whether we should consider non-parametric analyses. Only subjects with complete data from both pre-treatment assessment and 12-week assessment will be included in the final analysis. Data will be analyzed per an intent-to-treat approach regardless of actual treatment received. If a large proportion of missing data is noted, we will compare baseline characteristics of subjects who completed the treatment with those who were lost to follow-up.

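### Section 7.2 leaves Group 2 replaceable through the whole primary outcome window, and Group 2 participants who decide against acupuncture during the wait can drop out of the primary analysis

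*Combined protocol and SAP*

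**What the plan says.** Replacement (7.2) depends on one thing, whether the intervention was received. Before that, "Subjects who sign the informed consent form and are randomized but do not receive the study intervention may be replaced"; participants who "receive the study intervention, and subsequently withdraw, or are discontinued from the study, will not be replaced". Section 9.2 raises enrolment from 20 to 25 because "we wrote the protocol so that we could replace anyone who did not start the intervention", and the entry for version 7.0 in section 10.4 gives the same reason.

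Timing (6.1.2): "Group 1 will receive twice-weekly acupuncture immediately over 12-weeks"; "After a 12-week delay, Group 2 will also receive twice-weekly acupuncture over 12-weeks". No number of days from randomisation to session 1 is given for Group 1.

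Primary outcome (9.4.2): the change in MG-QOL15 over the first 12 weeks. In that period "Group 1 will have received the full acupuncture intervention between the two measurements while Group 2 will act as the untreated control". Group 2's second score is taken at Pre-treatment Visit 2, a phone call of about 20 minutes (section 1.3).

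Analysis set: section 9.3 states "All analyses will be performed on an intention-to-treat basis". Section 9.4.2 repeats the principle, whatever treatment was actually received, but admits only participants with both the baseline and the 12-week score.

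Withdrawal (7.1): a participant who chooses to stop the study or the study intervention is withdrawn from the study. A withdrawal call follows 7 to 14 days after the intervention stopped. Section 7.1 lists only adverse events for that call; the visit description in section 1.3 lists MG-QOL15 and MG ADL as well.

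**The concern.** A rule that looks the same for both arms acts differently in them, because receipt of acupuncture falls at the start of the primary window in Group 1 and after its end in Group 2.

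The person at issue is a Group 2 participant who decides, say, at week 6 not to go on to acupuncture. This person is needed only as an untreated control and could still give the week-12 score by phone. Under 7.1 the decision can be read as withdrawal from the study. The withdrawal call is then timed from the date the intervention stopped, a date that does not exist for someone never treated, and sections 1.3 and 7.1 disagree on whether the call collects MG-QOL15. Without a week-12 score, 9.4.2 excludes the participant, and 7.2 allows a replacement.

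Group 2 participants make this choice while seeing their own untreated course, in an open trial. If the choice is related to that course, the analysed controls are no longer a random half of those randomised. With about 10 per arm, one or two such losses matter. Replacement then restores the planned number, so the loss is less visible in the analysed counts.

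**Working it through.** **1. The plan's own figures.** For a two-sided two-sample t-test at alpha 0.05, with noncentrality d/√(1/n1 + 1/n2), 10 per group at d = 1.32 gives 79.7% power (9.2 states 80%). At d = 9.5/7 = 1.357, N = 16, 18 and 20 give 71.4%, 77.1% and 81.9% (stated 0.71, 0.77 and 0.82). The figures reproduce. The N = 18 and N = 16 rows correspond to 10% and 20% loss, which I use below. The plan's SD is 7.

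**2. How long each arm is replaceable.** Group 2: 12 × 7 = 84 days, plus the time from Pre-treatment Visit 2 to session 1. Group 1: not stated; I assume 3 to 14 days, because treatment starts at once. With a constant rate of leaving that totals 20% over 84 days, the share leaving within w days is 1 − 0.80^(w/84):
- Group 2, w = 84: 20%
- Group 1, w = 3: 0.8%
- Group 1, w = 14: 3.7%

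Replacement therefore refills almost only the control arm.

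**3. Size of the selection.** Assume no true effect, no loss in Group 1, a fraction d of controls lost before week 12, and correlation ρ between the tendency to leave and the untreated change. The mean of those who stay shifts by ρ × φ(z)/(1 − d) SD, with z the (1 − d) normal quantile. For d = 0.10, φ(1.282)/0.90 = 0.1755/0.90 = 0.195. For d = 0.20, φ(0.842)/0.80 = 0.280/0.80 = 0.350. Points are 7 × the shift. Type I error is from 40,000 simulated trials per setting, refilled to 10 controls and tested with the t-test of 9.2.

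| Loss in Group 2 | ρ | Shift (SD) | Shift (points) | Type I error |
|---|---|---|---|---|
| 10% | 0.3 | 0.058 | 0.41 | 5.2% |
| 10% | 0.5 | 0.097 | 0.68 | 5.6% |
| 10% | 0.7 | 0.136 | 0.96 | 5.8% |
| 20% | 0.3 | 0.105 | 0.73 | 5.6% |
| 20% | 0.5 | 0.175 | 1.22 | 6.5% |
| 20% | 0.7 | 0.245 | 1.71 | 8.3% |

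At ρ = 0 the shift is zero and the error stays at about 5%. The simulation error near 5% is √(0.05 × 0.95/40,000) = 0.1 percentage points, so 5.2% is barely distinguishable from nominal.

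**4. Which rule causes it.** The formula in step 3 contains no term for refilling: stayers have the same mean whether or not the leavers are replaced. An extreme case, again under no true effect, shows the same. Remove the most-improved controls, once from 10 with no replacement and once from 11, 12 or 13 so that 10 remain:

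| Controls removed | Bias, no replacement | Type I error | Bias, replaced | Type I error |
|---|---|---|---|---|
| 1 | 1.2 | 7.5% | 1.1 | 7% |
| 2 | 2.2 | 11.5% | 1.9 | 11% |
| 3 | 3.2 | 17.1% | 2.6 | 16% |

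If the removed controls are kept in the analysis, the bias is about zero and the error about 5%. The bias comes from losing the score and excluding the person. Abolishing replacement would not remove it.

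**The case against.** A reader might infer that the replacement rule itself biases the trial, above all through a Group 2 participant who gives the week-12 score, then declines acupuncture and is replaced. The documents do not support this. Section 9.4.2 admits participants by whether both scores exist and analyses them whatever treatment they received, so this person should already be analysed in Group 2. Nothing in 7.2 says that a replaced participant's data are discarded. What stands is that 7.2 still makes this person replaceable, and no sentence links replacement to the analysis set.

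A reader might also infer that a replacement is placed directly in the vacated arm. Section 5.5 says 25 people will be randomised, and 6.3 describes a single schedule that other study personnel cannot see in advance. Together these largely imply that additional participants take scheduled assignments; what is missing is an explicit sentence.

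Section 4.1 ("After a 12-week delay, 10 participants will receive acupuncture treatment") might suggest a target of 10 treated rather than 10 randomised per arm. That is an inference: 9.2 speaks of enrolling 10 per group, and 7.2 only permits replacement.

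The complete-case rule applies to both arms, and section 1.3 already seeks MG-QOL15 at early withdrawal. Both are true, but that call is not tied to week 12, and 7.1 does not list the score. The calculations use the t-test of 9.2, whereas 9.4.2 specifies a baseline-adjusted ANCOVA, so the sizes are illustrative.

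**Conclusion.** The point holds in a limited form and should be fixed. Replaceability ends at session 1 in Group 1 but runs through the whole primary window and past the endpoint visit in Group 2. Sections 7.1 and 9.4.2 together can remove Group 2 participants who decide against acupuncture during the wait. The main source of possible bias is the lost week-12 score with complete-case exclusion; one-sided replacement refills the arm and masks the loss.

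The range of about 0.4 to 1.7 points, with type I error of about 5.2% to 8.3%, rests on the plan's SD of 7, 10% to 20% loss in Group 2 only, and an assumed correlation of 0.3 to 0.7. The documents give no information on that correlation. The direction is unknown: if improvers leave, acupuncture looks better than it is; if those who worsen leave, it looks worse. If leaving is unrelated to outcome there is no bias. The error rates of 7% to 17% obtained by removing exactly the most-improved controls are a worst case and should not be read as expected.

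**What to change.** Amend 7.1, 7.2 and 9.2:

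1. A Group 2 participant who decides during the wait not to have acupuncture is still asked for the Pre-treatment 2 MG-QOL15 and MG ADL by phone at week 12, and is analysed in Group 2. Sections 1.3 and 7.1 must be reconciled on what the early withdrawal call collects, and the call needs a reference date that exists for someone never treated.
2. A Group 2 participant who has given the week-12 score has completed the primary outcome and is no longer replaceable, whether or not acupuncture follows.
3. Replaced participants with both scores stay in the analysis in their assigned arm. Any additional participant takes the next assignment in the existing randomisation schedule.

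The cost is protocol wording and a phone call that is already scheduled. Slightly fewer participants may receive acupuncture, because some will count toward the target without starting it. Participants who also refuse the call remain missing, so the loss is reduced but not abolished.

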7.3 LOST TO FOLLOW-UP

A participant will be considered lost to follow-up if he or she fails to attend any scheduled study visit and study staff are unable to contact the participant after at least 5 attempts, while maintaining the 7 day maximum between visits.

The following actions must be taken if a participant fails to attend any required study visit:

- Study staff will attempt to contact the participant, reschedule the missed visit, counsel the participant on the importance of maintaining the assigned visit schedule and ascertain if the participant wishes to and/or should continue in the study.
- Before a participant is deemed lost to follow-up, the investigator or designee will make every effort to regain contact with the participant (where possible, telephone calls or e-mail – if no answer leave a voicemail on the first and last attempt). These contact attempts will be documented.
- Should the participant continue to be unreachable, he or she will be considered to have withdrawn from the study with a primary reason of lost to follow-up.

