1.2 SCHEMA

1.3 SCHEDULE OF ACTIVITIES

	Pre-screening	Pre-treatment 1	Pre-treatment 2	Study Intervention	Post-treatment 1	Post-treatment 2	2-week follow up call
Group 1: Immediate Start	Visit 0	Visit 1	N/A	Visit 2-25	Visit 26	Visit 27	N/A
Group 2: Delayed Start		Visit 1	Visit 2	Visit 3-26	Visit 27	N/A	Visit 28
Review Eligibility	X						
Informed Consent		X					
Randomization		X					
Demographics		X					
Medication Review		X	X	X	X	X	
Symptom Severity Scale (Treatment Log)				X	X	X	X
MG-QOL15		X	X		X	X	
MG-ADL		X	X		X	X	
Adverse Events (AE) Reporting				X	X	X	X
Treatment Adherence				X			

VISIT SCHEDULE DESCRIPTION

All in-person visits will take place at: **HealthPartners Neuroscience Center, [name], HealthPartners Clinic St. Paul Como, [name], or Healing Response Acupuncture & Functional Neurology, [name].**

1. Pre-screening Phone Call (Groups 1 & 2)

- Duration: Approximately 30 minutes
- Research staff will:
 - Provide potential participants information about the study and ask whether they are interested in participating.
 - Determine whether they meet the inclusion/exclusion criteria for the study.
 - Ask participants for permission to communicate through e-mail for the study
 - Assist participants with setting up an e-mail account, if they do not have one.

- Schedule Pre-treatment Visit if the person is eligible for the study and e-mail the person the Informed Consent, Health Insurance Portability and Accountability Act (HIPPA), and HealthPartners non-discrimination forms.

2. Pre-treatment Visit 1 (Groups 1 & 2)

- Duration: Approximately 1 hour via phone
- Research staff will:
 - Review the Informed Consent and HIPPA documents with potential participants.
 - Answer any questions of potential participants and ensure they understand the expectations of the study.
 - Ask participants to electronically sign the Informed Consent and HIPAA documents via Research Electronic Data Capture (REDCap), a secure web-based system, and provide them electronic copies for their records.
 - Complete the Demographics and Medication Review short forms in the relevant electronic case report forms (eCRFs) in REDCap.
 - Interview patients using the Myasthenia Gravis Quality of Life Scale (MG-QOL15) and Activities of Daily Living (MG ADL) surveys and document in REDCap.

3. Pre-treatment Visit 2 (Group 2 only)

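### The lost-to-follow-up rule in Section 7.3 can fire at 24 treatment visits in Group 1 and at none in Group 2 before the second primary score, so temporary non-contact may cost the primary outcome in one arm only

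*Combined protocol and SAP*

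**What the plan says.** Section 7.3 declares loss to follow-up when a participant "fails to attend any scheduled study visit and study staff are unable to contact the participant after at least 5 attempts". The same sentence sets a limit on timing: "while maintaining the 7 day maximum between visits". Staff must first try to reschedule and to restore contact by phone or e-mail. If that fails, "he or she will be considered to have withdrawn from the study with a primary reason of lost to follow-up". The trigger is any scheduled visit, whether a treatment session or an assessment.

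The schedule in Section 1.3 places Group 1's acupuncture at Visits 2-25 and its second MG-QOL15 at Visit 26. Group 2 has its second MG-QOL15 at Visit 2, and its acupuncture follows at Visits 3-26. Both second-score visits are phone calls.

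Section 9.4.2 says the primary change "will be calculated using the first and second collected scores for both groups". It then restricts the data: "Only subjects with complete data from both pre-treatment assessment and 12-week assessment will be included in the final analysis". Section 9.3 states: "All analyses will be performed on an intention-to-treat basis".

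Three other places bear on this:
- Section 6.1.2 has treatments "separated by a minimum of 2 days and a maximum of 14 days", and Section 7.2 uses the same 14 days as a ground for discontinuation. Section 7.3 assumes 7 days.
- Section 7.1 withdraws from the study anyone who stops the intervention. It lists only the reason for stopping and adverse events as data to be collected.
- The early withdrawal call described under Section 1.3 does include the MG-QOL15 and MG ADL.

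**The concern.** Take two participants who are out of contact for the same two weeks in mid-period and then reachable again. The one in Group 1 misses sessions, cannot be reached, and can be classed as withdrawn. No section then schedules a 12-week MG-QOL15 for that person. The one in Group 2 has no visit to miss and gives the second score as usual. The same behaviour yields a missing primary outcome in one arm and a usable one in the other.

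Under a complete-case analysis, the comparison would then set Group 1 participants who stayed in contact against a less selected Group 2. That is no longer fully the randomised comparison that the intention-to-treat statement promises. If people who drop out of contact tend to do worse, the selection favours acupuncture. The loss is avoidable, because the outcome is collected by phone and does not depend on attending sessions.

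**Working it through.** **1. The plan's own power figures (Section 9.2).** Two-sided two-sample t-test, alpha 0.05, noncentral t with noncentrality d/√(1/n₁+1/n₂).
- 10 v 10 at 1.32 SD: 79.7% (stated 80%).
- Difference 9.5, SD 7 (1.357 SD): 71.4%, 77.1% and 81.8% at N = 16, 18 and 20 (stated 71%, 77%, 82%).

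These figures reproduce.

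**2. Opportunities for the rule to fire (Section 1.3).**
- Group 1: Visits 2-25 = 24 before the second score; with Visit 26, 25.
- Group 2: 0 before the second score; with Visit 2, 1.

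**3. Loss if each visit carries the same chance q (assumed; independent across visits).** Group 1 loss = 1 − (1 − q)²⁵; Group 2 loss = q.

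| q | Group 1 lost | Of 10 | Group 2 lost |
|---|---|---|---|
| 0.25% | 6.1% | 0.6 | 0.25% |
| 0.5% | 11.8% | 1.2 | 0.5% |
| 1% | 22.2% | 2.2 | 1% |

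**4. Temporary against permanent non-contact.** Assume a weekly chance h = 1% of becoming unreachable in either arm, and temporary spells of 2 weeks. Any spell can lose a Group 1 participant: 1 − 0.99¹² = 11.4%. In Group 2 a temporary spell matters only if it covers the second-score call: 1 − 0.99² = 2.0%. A permanent one always matters. With a fraction f permanent, Group 2 loss = f × 11.4% + (1 − f) × 2.0%.

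| Fraction permanent | Group 1 | Group 2 | Group 1 share of losses |
|---|---|---|---|
| 0 | 11.4% | 2.0% | 85% |
| 0.5 | 11.4% | 6.7% | 63% |
| 1 | 11.4% | 11.4% | 50% |

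The shares hardly move at h = 0.5% or 2%.

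**5. Shift in the Group 1 mean with no true effect.** Assume a normal tendency to be lost that correlates r = 0.5 with a poor change, and that the top fraction p is lost. The mean among those retained shifts by r·φ(z_p)/(1 − p).
- p = 0.06: 0.5 × 0.119 / 0.94 = 0.063 SD; × 7 = 0.44 points.
- p = 0.12: 0.5 × 0.200 / 0.88 = 0.114 SD; × 7 = 0.80 points.
- p = 0.22: 0.5 × 0.296 / 0.78 = 0.190 SD; × 7 = 1.33 points.

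The matching Group 2 shift is ignored; at 1% lost it is 0.5 × 0.0267 / 0.99 = 0.01 SD.

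**6. What that shift does to the test.** The standard error is √(1/9 + 1/10) = 0.459 SD for 9 v 10 and √(1/8 + 1/10) = 0.474 SD for 8 v 10. The shifts are 0.14, 0.25 and 0.40 standard errors (9, 9 and 8 v 10). The two-sided false-positive rate becomes 5.2%, 5.6% and 6.6% instead of 5%.

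**7. Power if two are lost from Group 1 only (8 v 10).** 74.3% at 1.32 SD; 76.6% at 9.5/7.

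**The case against.** A reader might infer that equal non-contact in the two arms removes people mainly from the acupuncture arm. The documents do not support that in general. Someone who stays unreachable misses the 12-week call in either arm, and step 4 shows the Group 1 share falling to 50% when all non-contact is permanent. Nor do they support a definite bias in favour of acupuncture. Group 2 has no scheduled contact for 12 weeks, which could raise its own losses at Visit 2, and nothing says that those lost do worse.

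The rule is also less abrupt than one missed session followed by silence. Section 7.3 requires real efforts to restore contact first, and Section 7.2 words discontinuation for loss to follow-up as permissive. This softens the rule without removing the problem: those efforts come before the declaration of loss, nothing calls for a fresh attempt at week 12, and discretion exercised in an unblinded trial is weak protection.

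The early withdrawal call might recover an MG-QOL15 from someone only briefly out of contact. But Section 7.1 limits its content to adverse events and makes up to 3 attempts, 7 to 14 days after discontinuation. Section 9.4.2 does not say whether such a score counts: it could be the second collected score, yet it is not a 12-week assessment. The comparison of baseline characteristics planned there, if much is missing, describes selective loss and does not repair it.

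Finally, a reader might infer an undisclosed loss of power. Section 9.2 already tabulates attrition, and 76.6% for 8 v 10 is close to its 77% at N = 18. The power point is secondary. The modest false-positive rates in step 6 also stand as a fair limit on the concern.

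**Conclusion.** The concern holds for temporary non-contact. As written, the rule has 24 chances to end follow-up in Group 1 before the second score and none in Group 2, and the complete-case analysis can turn this into differential loss of the primary outcome.

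The counts come from the schedule. Everything about size is assumed: the per-visit chance, independence across closely spaced visits (which makes the upper end generous), the mix of temporary and permanent spells, and the correlation of 0.5. On those assumptions 6% to 22% of Group 1 is lost, the mean shifts by 0.06 to 0.19 SD, and the false-positive rate reaches at most 6.6%. This is modest beside a 1.32 SD target, and its net direction is not established. It still deserves correction, because with 10 per arm one or two people are 10% to 20% of a group and the remedy is cheap.

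**What to change.** - In Section 7.3, and consistently in Sections 7.1 and 7.2, separate missing or stopping acupuncture from leaving the study. Changing Section 7.3 alone is not enough: under Section 7.2 a Group 1 participant untreated for more than 14 days can still be discontinued from the study, and Section 7.1 equates stopping the intervention with withdrawal.
- Unless consent is withdrawn, attempt the MG-QOL15 and MG ADL phone assessment at 12 weeks for every randomised participant, with the same number of attempts and the same calendar window in both groups. Declare the primary endpoint lost only if that call fails.
- In Section 9.4.2, include these scores in the intention-to-treat analysis, and state that an MG-QOL15 from the early withdrawal call does not replace the 12-week score.
- Reconcile the conflicting texts: the 7-day maximum in Section 7.3 against the 14 days in Sections 6.1.2 and 7.2, and the content of the early withdrawal call in Section 1.3 against Section 7.1. Which interval should govern treatment is for the investigators.

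The cost is a few paragraphs of text and some extra phone attempts at week 12, for perhaps one to three participants on the assumptions above. No extra visits or participants are needed.
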